## **7.8.2 Laboratory data**

The analyses of laboratory data will be descriptive in nature and will be based on BI standards (8).

Please refer to Section 7.3.4 of the CTP.

Kaplan-Meier plot for time to first liver enzyme elevation will be presented and displayed by treatment (if sufficient number of events).

Specific tables will be presented to describe liver enzyme elevations as defined in [Section 5.4.4](#) by treatment group:

- Summary table of liver enzyme elevation including time to first onset and number of patients with liver enzyme elevation.
- Kaplan-Meier plot of time to first liver enzyme elevation (if sufficient number of events). No statistical test will be performed. The time to event will be censored at EOT + 28 days. The Kaplan-Meier plots will present the time period until 24 weeks + 28 days.
- Summary table of individual maximum liver enzyme and bilirubin elevations
- Plot of time course profile of liver enzyme for patients having liver enzyme and bilirubin elevation

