4.2.1.3 Recommendations for managing liver enzyme elevations

For a detailed guidance on how to manage liver enzyme elevations, please refer to table 4.2.1.3: 1

Table 4.2.1.3: 1 Recommendations for managing liver enzyme elevations

AST /ALT ≥ 3 but < 5 x ULN		AST /ALT ≥ 5 but < 8 x ULN		Signs of hepatic injury ³
Reduce nintedanib to 100 mg bid or interrupt ² (at the discretion of the investigator) Lab tests ¹ at 48/72 hours, at 1 week and at 2 weeks		Interrupt ² nintedanib Lab tests ¹ at 48/72 hours, at 1 week and at 2 weeks		Permanently discontinue all study drugs
If AST /ALT < 3 x ULN within 2 weeks	If AST /ALT ≥ 3 ULN at 2 weeks	If AST /ALT < 3 x ULN within 2 weeks	If AST /ALT ≥ 3 ULN at 2 weeks	
Re-escalate nintedanib to 150 mg bid if reduced; restart at 100 mg bid if interrupted Lab tests ¹ at weeks 2 and 4	Interrupt ² both drugs Lab tests ¹ at weeks 1 and 2	Reintroduce nintedanib at 100 mg bid Lab tests ¹ at weeks 1, 2 and 4	Interrupt ² sildenafil Lab tests ¹ at weeks 1 and 2	
If AST / ALT ≥ 3 x ULN permanently discontinue nintedanib	If AST / ALT < 3 x ULN reintroduce drugs in a stepwise approach; lab tests ¹ every week as needed If AST / ALT ≥ 3 x ULN permanently discontinue all study drugs	If AST / ALT ≥ 3 x ULN permanently discontinue nintedanib	If AST / ALT < 3 x ULN reintroduce drugs in a stepwise approach; lab tests ¹ every week as needed If AST / ALT ≥ 3 x ULN permanently discontinue all study drugs	

¹ Laboratory tests include ALT, AST, total bilirubin, eosinophils, INR

² Treatment interruptions are allowed up to a maximum of 4 weeks.

³ Signs of hepatic injury are defined as:

- ALT and/or AST \geq 8 fold ULN
- ALT and/or AST \geq 3 fold ULN and total bilirubin \geq 2 fold ULN
- ALT and/or AST \geq 3 fold ULN and unexplained INR $>$ 1.5
- ALT and/or AST \geq 3 fold ULN and unexplained eosinophilia ($>$ 5%)
- ALT and/or AST \geq 3 fold ULN and appearance of fatigue, nausea, vomiting, right upper abdominal quadrant pain or tenderness, fever and/or rash.

For potential drug induced liver injury (DILI) follow up requirements please see [section 5.3.6.1](#).

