## **6.7 BASELINE, TIME WINDOWS AND CALCULATED VISITS**

For an overview on planned visits refer to Flow Chart in the CTP.

As a general rule, last assessment before first trial drug intake (included) will be used as baseline. If the baseline value is missing and the screening value is available, then the baseline value will be defined as the screening value taken closest to baseline date.

A windowing will be performed as described in [table 6.7:1](#) to [table 6.7: 6](#) in order to assign data to the relevant study visit based on the actual day of the assessment. Data will be analyzed using the re-calculated visits in the statistical tables. However, in the listings, all visits performed will be displayed (even if outside time-window), along with the re-calculated visit.

All visits, regardless whether study treatment is ongoing or not, and EOT visit are classified according to the time windowing rules. EOT is the day of the last trial drug administration (nintedanib and sildenafilfil/placebo).

Visits recorded as FUP visits will be classified according to the time windowing as given in the table for time windowing and will not keep their labeling “FUP”, unless they fulfill the conditions for the last category in the table.

If after windowing of visits at baseline, two values fall within the same baseline interval, then the last value will be taken into account. If after windowing of post-baseline visits, two visits fall in the same interval, then the measurement closest to the planned visit will be taken into account. In case two measurements are equidistant from the planned visit, then the last one will be picked. The same rules will be applied for laboratory measurements.

If after windowing of post-baseline visits, two values fall within the same interval “Follow-up”, then only the first value will be taken into account.

For visits of patients who continue to attend the scheduled study visits after early EOT visit the same rules apply as given above.

Table 6.7: 2 Time windowing rules for SGRQ, UCSD SOBQ, EQ-5D, Resting SpO2

Time window of actual day [1]			Allocated to		
Start day	End day (included)	Length of the time-window [days]	Visit number	Visit name	Planned day of the visit
1	1	1	2	Baseline	1
2	57	56	3	4 weeks	29
58	127	69	5	12 weeks	85
128	No limit		7	24 weeks	169

[1] First trial drug intake date is taken into account as a reference to calculate time windows

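### Read literally, the SAP's one-value-per-window rule would keep most repeat liver tests out of the maximum and first-elevation outputs; the SAP should state that these use all on-treatment values

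*SAP*

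**What the plan says.** **SAP 6.7** sets the data-selection rule in four steps.

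- Assessments are assigned to a study visit by their actual day, and "Data will be analyzed using the re-calculated visits in the statistical tables".
- Where, after baseline, "two visits fall in the same interval, then the measurement closest to the planned visit will be taken into account"; if two are equally distant, the later one is used.
- "The same rules will be applied for laboratory measurements".
- Listings are treated differently: they show every visit, including those outside a window. This is the only visible place where unselected values are said to appear.

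**SAP 7.8.2** plans the liver outputs: a table with time to first onset and the number of patients with elevation, a Kaplan-Meier plot of time to first elevation, a "Summary table of individual maximum liver enzyme and bilirubin elevations", and time-course plots. It refers to SAP 5.4.4 for the definition of elevation and to a sponsor standard for laboratory analyses.

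**Protocol Table 4.2.1.3:1** requires further tests "at 48/72 hours, at 1 week and at 2 weeks" once AST or ALT reaches 3 x ULN without signs of hepatic injury. Protocol 5.3.3 expects more frequent sampling when values suggest toxicity, and the flow chart schedules laboratory tests at dose adjustment visits.

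**The concern.** A maximum and a first onset are meant to be taken over everything that was measured. The repeat tests are the samples that show whether an enzyme rise went on to a higher band. A rule that picks one value by its distance from a calendar day ignores severity, and it favours the scheduled sample over the repeats that follow it.

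The summary tables in 7.8.2 are statistical tables, and 6.7 says such tables use the re-calculated visits. A programmer who followed 6.7 to the letter would compute each patient's maximum from the retained values only.

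Liver enzyme elevation is a named nintedanib risk. Protocol 2.2 puts the safety of the combination in the primary objective, and protocol 2.3 says it is unknown whether co-administration brings additional side effects. The by-arm maximum table is a main place where a reader would look for this.

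**Working it through.** The plan gives no figure to reproduce. The check applies the 6.7 rule to the protocol's test schedule.

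**Inputs**

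- Scheduled post-baseline laboratory days: 29, 57, 85, 127, 169 (protocol flow chart).
- Repeats after a trigger on day *d*: *d*+2 or *d*+3, *d*+7, *d*+14 (protocol Table 4.2.1.3:1).
- Laboratory windows: not visible, so **assumed** to run to the midpoints between planned days. Table 6.7:2 follows this pattern: (29+85)/2 = 57 and (85+169)/2 = 127 are its window ends. For the laboratory days the midpoints are (29+57)/2 = 43, (57+85)/2 = 71, (85+127)/2 = 106 and (127+169)/2 = 148.
- Rule: within a window keep the value with the smallest |day − planned day|.

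**1. Elevation found on the planned day**

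| Trigger day | Assumed window | Repeat days | Kept | Dropped |
|---|---|---|---|---|
| 29 | 2–43 | 31/32, 36, 43 | 29 | all 3 repeats |
| 57 | 44–71 | 59/60, 64, 71 | 57 | all 3 repeats |
| 85 | 72–106 | 87/88, 92, 99 | 85 | all 3 repeats |
| 127 | 107–148 | 129/130, 134, 141 | 127 | all 3 repeats |
| 169 | 149 onward | 171/172, 176, 183 | 169 | all 3 repeats |

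The trigger has distance 0 and the repeats have distances 2 or 3, 7 and 14. One of four values is kept. A maximum over this subset can equal the maximum over all values or be lower; it cannot be higher. The trigger itself is retained, so the patient is still counted as elevated and the onset is not delayed.

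**2. Trigger displaced within the visit tolerance**

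The flow chart allows ±3 days at week 4. A trigger on day 26 has distance 3. Its 48-hour repeat on day 28 has distance 1, and a 72-hour repeat on day 29 has distance 0. Either way the repeat is kept and the trigger is dropped. If the repeat has already fallen below the limit set in 5.4.4, and no other retained value is raised, the patient leaves the elevation count.

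**3. First elevation in an unscheduled sample**

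With the scheduled sample on its planned day (distance 0), raised values on days 10, 20, 40, 70, 105 and 150 have distances 19, 9, 11, 13, 20 and 19. All are dropped. The elevation is then missed, or dated to a later retained value if that is also raised.

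**4. What the other outputs would still show**

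Protocol 5.3.6.1 defines hepatic injury as ALT/AST ≥8 x ULN, or ≥3 x ULN with a bilirubin, INR, eosinophil or symptom criterion. These are adverse events of special interest and have their own table (SAP 7.8.1). An isolated peak of 5 to <8 x ULN meets neither part, although protocol Table 4.2.1.3:1 treats it as a separate category. The liver adverse event groupings in SAP Table 7.8.1:1 carry no ULN multiples. A patient with 3.5 x ULN at a visit and a peak in the 5 to <8 band at the one-week recheck would therefore appear as 3.5 x ULN in the maximum table, and the peak would be visible only in the listings.

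**The case against.** The strongest reply is that 6.7 is a rule for allocating data to visits and was never meant for outputs that have no visit. An individual maximum belongs to no visit, and time to first elevation runs on days: "The time to event will be censored at EOT + 28 days". SAP 6.1 treats safety data up to 28 days after the last intake as on-treatment, with no mention of one value per visit. On this reading both outputs use all values. That is a fair guess at the intent, but the visible text does not say it, and 6.7 names both statistical tables and laboratory measurements.

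Second, SAP 5.4.4, the laboratory window table and the sponsor laboratory standard are not in the text available, and any of them may hold an exception. This stands in full. It means the point can only be conditional.

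Third, other outputs catch severe cases. This stands for values of 8 x ULN or more and for the combined hepatic-injury criteria. It does not cover the 5 to <8 x ULN band as a by-arm summary.

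Fourth, the outputs are descriptive, no test depends on them, and the same rule applies to both arms. This is correct and limits the weight of the point.

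A reader might infer that the repeats are in fact discarded and that the trial understates liver toxicity. The documents do not support that: the sections that could settle it are not visible, and the listings, the special-interest table and the liver adverse event tables remain.

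**Conclusion.** The point holds conditionally. If 6.7 is applied as written to the 7.8.2 liver outputs, most repeat and unscheduled ALT, AST and bilirubin values would be left out. The maximum table could be too low, chiefly for isolated peaks of 5 to <8 x ULN. The elevation count and the Kaplan-Meier plot are affected more narrowly: only where the first raised value is unscheduled, or is displaced by a repeat nearer the planned day.

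The one-in-four count rests on the assumed midpoint windows. The direction does not: within any window only one value survives, and it is chosen by day and not by level. The size of any understatement cannot be computed, because the documents give no ALT/AST rates or time course; a percentage would only reflect invented enzyme kinetics. The point is worth correcting because the rule as stated can give a wrong maximum in a key safety table and the remedy is close to free. It bears on no efficacy conclusion.

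**What to change.** Add to SAP 6.7, and repeat or cross-reference in 7.8.2, wording such as: *The one-value-per-window rule applies only to by-visit laboratory summaries. Individual maximum values, number of patients with elevation, time to first elevation and time-course plots use all on-treatment values up to 28 days after the last intake, including repeat, unscheduled and dose adjustment visit samples.* If 5.4.4 or the sponsor laboratory standard already says this, a cross-reference is enough.

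The wording should also make clear that samples taken while a drug is interrupted are included. SAP 6.1 defines a separate off-treatment period for interruptions, and many of the required repeats may fall in it.

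The cost is one sentence, with no new data collection. There is a small downside: patients who are retested more often have more chances to show a peak.

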### **7.8.3 Vital signs**

Only descriptive statistics (by visit and change from baseline) are planned for this section of the report.

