In such cases, continuation of nintedanib should be discussed with the patient and the decision based on an individual benefit-risk assessment documented in the source data.

Treatment with sildenafil/matching placebo must be permanently discontinued in the following situations:

- In the opinion of the investigator, the patient experiences unacceptable toxicity due to sildenafil despite supportive care;
- Hypotension (SBP < 100 mmHg or DBP < 50 mmHg) accompanied by symptoms;
- In the event of any sudden visual defect;
- Prolonged erections and priapism;
- Treatment interruption longer than 4 weeks (continuous).

If a patient discontinues all study drugs (nintedanib and sildenafil/matching placebo), he/she will undergo the procedures for early treatment discontinuation and will be invited to attend all planned study visits until week 24 as outlined in the [flow chart](#).

For all patients the reason for withdrawal (e.g. adverse events) must be recorded in the electronic case report form (eCRF). These data will be included in the trial database and reported.

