5.3.2 Vital Signs

Vital signs, including measurements of systolic and diastolic blood pressure and pulse rate, will be measured with the patient seated after having rested for at least 5 minutes.

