## **6. GENERAL ANALYSIS DEFINITIONS**

### **6.1 TREATMENTS**

The following trial periods will be defined: screening, post-randomisation, treatment period, off-treatment, residual effect period, follow-up and post-study as follows:

Note: the last day of each of the following periods is excluded.

- Screening: from informed consent to randomisation
- Post-randomisation (optional): from randomisation to first randomised trial drug intake in treatment period
- Treatment period: from first randomised trial drug intake (or re-start of treatment if interruption) to last randomised trial drug intake (or the day before start date of interruption, if interruption) plus one day
- Off-treatment (optional): from start date of interruption to re-start of treatment
- Residual effect period (optional): from the last trial drug intake plus one day to last trial drug intake plus 28 days plus one day
- Follow-up (optional): from last trial drug intake plus 29 days up to the beginning of post-study period. This period is only created if last trial drug intake took place more than 28 days before trial completion, or for patients having prematurely discontinued the treatment and still continuing the trial

- Post-study: from the latest of last trial drug intake plus 29 days / date of trial completion / follow-up visit / early end of treatment visit plus 1 day to database lock

For safety analyses, data up to 28 days after last trial drug intake (included) will be considered on-treatment. For on-treatment efficacy analyses, data up to the day after last trial drug intake (included) will be considered.

For safety and efficacy analyses, patients will be assigned to the treatment group they were randomised to.

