## **7. PLANNED ANALYSIS**

For End of Text tables, the set of summary statistics is: N / Mean / SD / Min / Median / Max.

Tabulations of frequencies for categorical data will include all possible categories and will display the number of observations in a category as well as the percentage (%) relative to the respective treatment group (unless otherwise specified, all patients in the respective patient set whether they have non-missing values or not). Percentages will be rounded to one decimal place. The category missing will be displayed as the last category only if there are actually missing values.

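### The vital-signs plan gives no by-arm count of patients whose measured blood pressure falls below the protocol's own hypotension limit

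*SAP*

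**What the plan says.** Protocol 5.3.2 defines what is measured: "Vital signs, including measurements of systolic and diastolic blood pressure and pulse rate", taken seated after rest. The flow chart marks vital signs at every visit, including dose adjustment, early end-of-treatment and follow-up visits.

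The protocol uses one numerical limit twice. Exclusion criterion 14 applies SBP < 100 or DBP < 50 mmHg at visit 1. Protocol 3.3.4.1 lists among the reasons for permanently stopping sildenafil/placebo: "Hypotension (SBP < 100 mmHg or DBP < 50 mmHg) accompanied by symptoms".

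For the analysis, SAP 7.8.3 is a single sentence: "Only descriptive statistics (by visit and change from baseline) are planned for this section of the report". SAP 7 adds that for end-of-text tables "the set of summary statistics is: N / Mean / SD / Min / Median / Max". Protocol 7.3.4 promises frequencies of abnormal values for laboratory data, but for vital signs only an assessment of possible changes from before treatment.

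Two general rules in SAP 6.7 bear on which readings enter a by-visit table. When after windowing "two visits fall in the same interval, then the measurement closest to the planned visit will be taken into account". And "All visits, regardless whether study treatment is ongoing or not, and EOT visit are classified according to the time windowing rules". SAP 6.1 adds that for safety analyses "data up to 28 days after last trial drug intake (included) will be considered on-treatment".

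**The concern.** A drug-induced fall in blood pressure may affect only a few patients. Mean, SD and median respond weakly to that pattern. The minimum shows that at least one patient was low, but not how many. The natural summary is the number of patients below a limit, and the protocol already supplies the limit.

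Safety is part of the primary objective (Protocol 2.2), and Protocol 2.3 says it is unknown whether the combination brings additional side effects. Measured blood pressure is the one source on this risk that does not depend on an investigator deciding to report an event. For liver enzymes the SAP does work at patient level, with a "Summary table of individual maximum liver enzyme and bilirubin elevations" and a count of patients with elevations. The visible text has no counterpart for blood pressure, and the adverse event groupings in SAP Table 7.8.1:1 include hypertension but no hypotension topic.

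**Working it through.** The documents state no figure for this point, so there is none to reproduce. The check has three steps.

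**1. What each route captures**

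| Kind of low reading | Where it appears | Compared by arm? |
|---|---|---|
| Symptomatic, leads to stopping or interrupting sildenafil/placebo | Adverse event tables for discontinuation or interruption (SAP 7.8.1) | Yes |
| Judged clinically relevant by the investigator | Recorded as an adverse event (Protocol 5.3.7) | Yes |
| Below the limit, not judged clinically relevant | Listing; the lowest value per visit and arm appears as the minimum | No count |

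The gap is the third row.

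**2. What the planned statistics can show**

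The documents give no blood pressure distribution, so these inputs are assumptions: 125 patients per arm (the planned size), SBP at one visit normal with mean 120 to 130 and SD 12 to 15, and a share f of 5% or 10% of sildenafil patients falling by 25 mmHg. The model ignores truncation from the entry criterion.

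- Shift in arm mean = f × 25: 0.05 × 25 = 1.25 mmHg; 0.10 × 25 = 2.5 mmHg.
- Control share below 100 = Φ((100 − mean)/SD). At mean 125, SD 15: Φ(−1.67) = 0.048, and 125 × 0.048 = 6.0 patients.
- Sildenafil share = (1 − f) × control share + f × Φ((100 − (mean − 25))/SD). At mean 125, SD 15 the last term is f × 0.5. For f = 5%: 0.95 × 0.048 + 0.025 = 0.070, or 8.8 patients. For f = 10%: 0.90 × 0.048 + 0.05 = 0.093, or 11.6 patients.
- Probability that the printed control minimum is below 100 = 1 − (1 − share)^125.

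| Assumed mean / SD | Control, expected n < 100 | Sildenafil, f = 5% | Sildenafil, f = 10% | P(control minimum < 100) |
|---|---|---|---|---|
| 120 / 15 | 11.4 | 14.8 | 18.1 | 1.000 |
| 125 / 15 | 6.0 | 8.8 | 11.6 | 0.998 |
| 130 / 15 | 2.8 | 5.0 | 7.2 | 0.944 |
| 125 / 12 | 2.3 | 5.3 | 8.3 | 0.904 |

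In the sildenafil arm the minimum is below 100 with probability 0.994 or more throughout. Both arms will therefore almost always print a minimum below 100 mmHg. The table would show that someone was low, but not how many or in which arm there were more.

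**3. Which readings enter**

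The general SAP 6.7 rule drops a reading from the tables only when another in the same window is closer to the planned day, or equally close and later. It also keeps readings taken off treatment. The clearest case is a patient who stops sildenafil/placebo but stays on nintedanib. No early end-of-treatment visit is triggered, because that applies when all study drugs stop. Scheduled visits continue, and the later readings, taken without sildenafil (half-life about 4 hours, Protocol 1.2.2), enter the by-visit summary. SAP 6.7 refers to Tables 6.7:1 to 6.7:6, of which only 6.7:2 is visible, and that one does not cover vital signs. The size of either effect cannot be calculated.

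**The case against.** The strongest reply is that hypotension that matters clinically is already covered. The stopping rule requires symptoms, so such cases should appear as adverse events leading to discontinuation. Clinically relevant vital-sign changes must be reported as adverse events, failure to stop when the criteria are met is an important protocol violation (C6 in SAP Table 6.2:1), and the DMC reviews unblinded safety data. All of this stands, and it confines the point to low readings that no one judged relevant.

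A second reply is that a count would be little more sensitive than the mean. On one set of assumed values (4.1% below 100 mmHg in control against 5.5% to 9.6% on sildenafil), a 95% interval for the difference in proportions excludes zero in about 8% to 42% of trials, against about 8% to 33% for the mean change. This also stands. The case for the count is that it describes the harm in patients, not that it is a powerful test. Safety here is descriptive in any case.

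A third reply is that parts of both documents are not visible, including Protocol 7.3.3 and most of the SAP 6.7 windowing tables. A count could be specified there, so the point is limited to the visible text.

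A reader might go further and infer that blood pressure is summarised only by means, that off-schedule readings are discarded in general, or that hypotension will not show at all. The documents do not support this: minimum and median are printed, all visits performed are listed, and a reading is dropped only when another in its window is preferred. Nor do they say that the blood pressure schedule was chosen because of sildenafil's hypotension risk.

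**Conclusion.** The point holds in limited form. In the visible text, no table compares the arms on how many patients had measured blood pressure below the protocol's own limit. What escapes comparison is low readings not judged clinically relevant. On the assumed values above, the difference at stake is roughly 2 to 7 patients per 125 at a visit, accompanied by a shift in the mean of 1.25 to 2.5 mmHg; none of these figures comes from the trial documents. The windowing rules add an uncertainty of unknown size about which readings the by-visit table reflects.

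This does not affect the primary analysis and does not mean that hypotension goes unmonitored. It is worth changing because a more informative summary is available at very little cost.

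**What to change.** Add one table to SAP 7.8.3, by randomised arm:

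- n (%) of patients with any post-baseline SBP < 100 mmHg or DBP < 50 mmHg, using the limit already in the protocol;
- each patient's lowest post-baseline SBP and DBP, and largest fall from baseline, summarised with the SAP 7 statistics.

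Derive these from all scheduled and unscheduled readings, before the closest-to-planned-visit selection. Show readings up to the last sildenafil/placebo dose separately from later ones, so that values after sildenafil alone was stopped can be recognised. Leave the planned by-visit table and the 28-day safety period as they are.

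The cost is some SAP wording and one extra table from data already collected, with no new assessment and no change to patient management. The downside is that isolated low seated readings without symptoms will be counted, so the table should be read beside the adverse event tables.
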